7.2 SERIOUS ADVERSE EVENT

A **serious** adverse event (SAE) is any adverse event occurring after signing informed consent at any dose that suggests a significant hazard or side effect, regardless of the investigator or sponsor's opinion on the relationship to the investigational product and that results in, but may not be limited to, any of the following outcomes:

- Death (regardless of the cause)
- Life-threatening adverse drug experience
- Inpatient hospitalization or prolongation of existing hospitalization (any inpatient hospital admission that includes a minimum of an overnight stay in a health care facility)
- Persistent or significant disability/incapacity
- Congenital anomaly or birth defect.

Important medical events that may not be fatal, life threatening, or require hospitalization may be **serious** when, based upon appropriate medical judgment, they may jeopardize the patient and may require medical or surgical intervention to prevent one of the outcomes listed above.

Hospitalization for elective treatment of a pre-study condition that did not worsen while on study and hospitalizations for treatment of non-adverse events (e.g., cosmetic surgery) are not considered serious adverse events. Situations where an untoward medical occurrence did not occur (e.g., social and/or convenience admission to a hospital) are not considered as serious adverse events.

The underlying medical condition for any surgery performed should be reported as the event term rather than the procedure itself.

Significant medical events are those which may not be immediately life threatening, but may jeopardize the patient and may require intervention to prevent one of the other serious outcomes listed above. Examples of such events are intensive treatment in an emergency room or at home for allergic bronchospasm; blood dyscrasias or convulsions that do not result in hospitalization; resulting in an adverse event which would normally be considered serious by this criterion.

Inpatient hospitalization or prolongation of existing hospitalization refers to hospital inpatient admission and/or prolongation of hospital stay required for treatment of AE, or which occurred as a consequence of the event. Hospitalization for elective treatment of a pre-study condition that did not worsen while on study and hospitalizations for treatment of non-adverse events (e.g., cosmetic surgery or diagnostic procedure) are not considered serious adverse events.

Any new SAE that occurs up to 30 days after the study period and is considered related (possibly/probably) to the investigational product or study participation should be recorded and reported immediately.

A **life-threatening** adverse drug experience is any adverse event that places the patient, in the view of the investigator, at immediate risk of death from the reaction as it occurred, i.e., it does not include a reaction that, had it occurred in a more severe form, might have caused death.

Every attempt should be made to describe the AE/SAE in terms of a diagnosis. However, if an observed or reported sign or symptom is not considered a component of a specific disease or syndrome by the Investigator, it should be recorded as a separate AE/SAE on the eCRF. Once a clear diagnosis has been made, individual signs and symptoms shall not be recorded unless they represent atypical or extreme manifestations of the diagnosis, in which case they should be reported as separate events. If a clear diagnosis cannot be established, each sign and symptom must be recorded individually.

7.3 DEFINITION OF AN UNEXPECTED ADVERSE EVENT

An **unexpected** adverse drug experience (event) is any adverse event of specificity or severity not reported in the current Investigator's Brochure.

7.4 NOTIFICATION ABOUT SERIOUS OR UNEXPECTED ADVERSE EVENTS

All SAEs must be reported **immediately** to the Immune Pharmaceuticals representative as soon as it becomes known to the investigator and not later than within 24 hours of their knowledge of the occurrence of an SAE.

Immune Pharmaceuticals Representative:

Telephone:	ext
Mobile:	
Fax:	
E-mail:	

These preliminary reports will be followed within 24 hours by detailed descriptions that will include a completed SAE form, copies of hospital case reports, autopsy reports, and other documents, when requested and applicable.

In addition, all AEs/SAEs/Suspected Unexpected Serious Adverse Reaction (SUSARs) will be reported to the local EC and regulatory authorities as required by local regulations and ICH-GCP guidelines.

Preliminary Reports must include:

- An identifiable patient (e.g., subject number)
- An identifiable reporting source
- All related adverse events
- The suspect medicinal product
- Follow-up of SAEs/SUSARs

Follow-up of SAEs/ SUSARs that occur during the study will continue until satisfactory resolution or stabilization.

If and when supplementary information is available, a follow-up SAE Report Form must be completed by the site and faxed within 24 hours to Sponsor.

The contact information for follow up SAE reporting is the same as for initial SAE reports (see Section 7.4).

Once faxed, the SAE form and accompanying documentation should be placed in the SAE section of the investigator's file. If supplementary information on a SAE has to be sent, the SAE form has to be used marked as "Follow-Up Report."

SAEs may be reported through an EDC system with a paper form used as back up.

Follow-Up Reports on non-serious AE

All AEs must be followed until resolution or stabilization. In outstanding cases, it may be defined as "ongoing without further follow-up" by the investigator and sponsor's decision.

8.0 STATISTICAL ANALYSIS

This is an open-label study. Thus, only descriptive statistics are planned. All data collected on the case report forms (CRFs) will be summarized for the clinical study report (CSR).

All continuous parameters will be summarized using standard summary statistics as appropriate (n, mean, standard deviation, median, minimum, maximum, 25th percentile, and 75th percentile).

Summary statistics for categorical variables will include frequency counts and percentages. Summaries will be presented for all patients and by Treatment Phase and Follow-up Evaluation.

Details will be specified in the statistical analysis plan.

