5.11 POST TREATMENT PHONE CALL

Approximately 2 and 4 months after Visit 8 (Day 84), a follow-up phone call will be placed and the following assessments will be performed: completion of ABQOL questionnaire, adverse event assessment, and concomitant medication reporting. Corticosteroid usage (oral and topical) will be documented and managed as necessary.

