### 9.3.1 Main Safety Analysis

### **Treatment Related AEs**

- Adverse Events that are possibly or probably related to treatment (including serious) will be tabulated using frequency tables with - Number of Subjects and Percentage of Subjects by:
  - Overall by System Organ Class (SOC) and Preferred Term
  - Maximal Severity by System Organ Class (SOC) and Preferred Term
  - By subject listing of treatment related Adverse Events

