### **Serious Adverse Events (SAEs):**

All SAEs will be tabulated using frequency tables with - Number of Subjects and Percentage of Subjects by:

- Overall by System Organ Class (SOC), Preferred Term and maximal severity
- Overall by System Organ Class (SOC), Preferred Term and maximal relation to study drug
- By subject listing of SAEs

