### **Infusion Reaction Assessment (including injection site reactions)**

 By subject listing of any infusion reactions (all responses except "no reaction"), including visit and time point.

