### **Adverse Events (AEs):**

All Adverse Events (including serious) will be tabulated using Frequency tables with -Number of Incidents, Number of Subjects and Percentage of Subjects by:

- Overall by System Organ Class (SOC) and Preferred Term
- Severity by System Organ Class (SOC) and Preferred Term
- Relation to study drug by System Organ Class (SOC) and Preferred Term
- Severity and Relation to study drug

• By subject listing of Adverse Events

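### The SAP's adverse-event tables omit the protocol's split by treatment phase and follow-up, and none is limited to treatment-emergent events

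*Protocol*

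**What the plan says.** Protocol 8.0, repeated in the synopsis, states: "Summaries will be presented for all patients and by Treatment Phase and Follow-up Evaluation". It then adds: "Details will be specified in the statistical analysis plan".

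The SAP's adverse-event outputs are these:

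- Related AEs (9.3.1): "Adverse Events that are possibly or probably related to treatment (including serious) will be tabulated using frequency tables", giving number and percentage of subjects overall and as "Maximal Severity by System Organ Class (SOC) and Preferred Term".
- SAEs (9.3.1): "All SAEs will be tabulated using frequency tables", with maximal severity and maximal relation to study drug.
- All AEs (9.3.2): "All Adverse Events (including serious) will be tabulated using Frequency tables", giving incidents, subjects and percentages by severity and relation.
- Infusion reactions (9.3.1): "By subject listing of any infusion reactions", with visit and time point.

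The first three have no phase column, no time at risk and no end to the window. SAP 7.1.2 names treatment-emergent AEs, meaning those starting at or after first dosing, as an additional endpoint, but no table in section 9.3 is limited to them. Vital signs, physical examination, ECG and anti-drug antibodies are presented by visit.

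Under Protocol 5.3.1, AE recording starts when consent is signed, and screening may begin on Day -28. It continues through the post-treatment calls of Protocol 5.11: "Approximately 2 and 4 months after Visit 8 (Day 84), a follow-up phone call will be placed". Appendix A places these at about Days 144 and 204.

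**The concern.** Safety is the primary objective and there is no control arm. The timing of an event relative to an infusion is therefore the main internal evidence for separating a drug effect from background illness in patients aged 60 or older. A single percentage over the whole period removes that information from the summary tables. Because the tables are not restricted to treatment-emergent events, those for SAEs and all AEs can also count events that began before any drug was given.

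A percentage without patient-days also hides unequal observation. Early discontinuation is one possible source. Another is that the calls were added in protocol version 6.0, while the SAP (6.2.1 and the prednisone section of 7.2.1) refers to more than one protocol version in use. The documents do not say how many patients, if any, lacked the calls.

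**Working it through.** **Inputs.** Infusions on Days 0, 14 and 28 (Protocol 3.0). Last clinic visit for all patients on Day 84. Calls 2 and 4 months later (Protocol 5.11). Screening from Day -28. Mean half-life 194 h after 10 mg/kg (CV 27.1%) and 211 h after 5 mg/kg (Protocol 1.3.1). At most 15 patients.

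**1. The plan's own duration.** With 30-day months, 84 + 2 × 30 = 144 and 84 + 4 × 30 = 204. Both agree with Appendix A and the synopsis.

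**2. Shares of person-time for a patient followed to Day 204.**

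| Window | Days | Share of Days 0–204 | Share from Day -28 (232 days) |
|---|---|---|---|
| Pre-dose | 28 | – | 28/232 = 12.1% |
| Day 0–28 | 28 | 28/204 = 13.7% | 28/232 = 12.1% |
| Day 28–84 | 56 | 56/204 = 27.5% | 56/232 = 24.1% |
| After Day 84 | 120 | 120/204 = 58.8% | 120/232 = 51.7% |

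**3. Drug remaining.** Assume first-order decay with a single half-life. The fraction of the post-third-dose concentration left t hours later is then 2^(−t/half-life). Day 84 is 56 × 24 = 1,344 h after the third infusion.

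- 194 h: 1,344/194 = 6.93 half-lives, leaving 0.8%.
- 211 h: 1,344/211 = 6.37 half-lives, leaving 1.2%.
- Two SD above the 194 h mean: 194 × (1 + 2 × 0.271) = 299 h and 1,344/299 = 4.49 half-lives, leaving about 4%.

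At Day 42 (336 h) the fraction is still 30% at 194 h and 33% at 211 h, so the start of the follow-up period is not drug-free.

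**4. What this means for percentages of subjects.** The related-AE and SAE tables count subjects, not days. Suppose the hazard is constant and a proportion P of patients has an event by Day 204. The proportion affected by Day 84 is 1 − (1 − P)^(84/204). Dividing by P gives the share of affected patients whose first event falls by Day 84.

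| P (assumed) | Affected by Day 84 | Share of affected patients |
|---|---|---|
| 10% | 4.2% | 42% |
| 50% | 24.8% | 50% |
| 80% | 48.5% | 61% |
| 95% | 70.9% | 75% |

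For counts of events, an early rate 120/84 = 1.43 times the late rate would already split them equally at Day 84. The documents give neither incidence nor hazard, so the balance of early and late events is unknown.

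**5. Which outputs are affected.** Protocol 5.3.6 limits infusion-reaction assessment to dosing visits, and the SAP lists reactions by visit and time point, so they are not pooled. Protocol 7.1 bases the possible and probable categories on timing after administration and places events without a plausible sequence under unlikely, which filters the related-AE table. The SAE and all-AE tables have no such filter.

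**The case against.** The sentence in Protocol 8.0 is general. It does not name adverse events, and it leaves detail to the SAP, which does show repeated measurements by visit across treatment and follow-up. That could be read as meeting the commitment. It is a fair reading for visit-based data, but it does not account for AEs and SAEs, which have no visit dimension in the SAP and for which no reason is given.

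With at most 15 patients, little can stay hidden. By-subject listings are planned for related AEs, SAEs and all AEs, all CRF data are listed (SAP 10), and the synopsis plans patient narratives. A reader could reconstruct timing by hand. This stands and limits the harm, but listings are not the promised summaries.

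A reader might infer from the 59% share that the reported safety rates are dominated by months with almost no drug present. The documents do not support that:

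- The share is of person-time, and the subject percentages depend on hazards that are not given.
- After Day 84, AEs are collected at two calls plus Visit 9 where applicable, so late events may be under-recorded.
- Protocol 1.3.1 reports strong inhibition 35 days after a dose, which is Day 63 counted from the third infusion. Low concentration is therefore not the same as absence of effect.

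**Conclusion.** The point holds as a gap between protocol and SAP on the primary objective. The by-phase presentation is not carried into any AE or SAE table, and the treatment-emergent definition is not applied to any of them. The SAE and all-AE tables can combine up to 28 pre-dose days with follow-up to about Day 204. Of the post-dose time, 14% is the treatment period and 59% lies after Day 84, when about 1% of the post-third-dose concentration remains.

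The concentration figure assumes single-half-life decay, with values from a single-dose study in healthy volunteers. The time shares assume that a patient is followed to Day 204. Neither shows that any reported percentage would be misleading. The point does not extend to infusion reactions and applies only weakly to related AEs. It is a low-cost improvement in presentation, and no decision rule in the plan depends on it.

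**What to change.** In SAP 9.3.1 and 9.3.2:

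- Restrict the main AE and SAE tables to treatment-emergent events as defined in SAP 7.1.2, and list pre-dose events separately.
- Beside the overall column, add columns by onset: from the first infusion up to the third (Day 28), from the third infusion to Day 84, and after Day 84. Give patients at risk and patient-days for each. The last two columns together correspond to the protocol's follow-up.
- Assign events starting after the third infusion to the second window. State a rule for Day 28 events without an onset time and for patients who do not receive the third infusion.
- Add days since the last infusion to the AE listings, so that clustering after any of the three infusions stays visible.
- If the sponsor prefers not to split the tables, say so in the SAP and give the reason.

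No new data are needed. Protocol 7.1 already requires dates and times of occurrence, and SAP 6.1 refers to a CRF field for the date of drug administration. The cost is a little programming and small cells, since there are at most 15 patients; the overall column should stay for that reason.

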9.0 ETHICS

9.1 INSTITUTIONAL REVIEW BOARD OR INDEPENDENT ETHICS COMMITTEE

Prior to initiation of the study, the investigator will submit the study protocol and amendments, sample Informed Consent Form (ICF), and any other documents that may be requested to the IRB/IEC for review and approval. The investigator will request that the IRB/IEC provide written approval of the study and will keep on file records of approval of all documents pertaining to this study. The investigator will not begin the study until the protocol and ICF have been approved by the IRB/IEC. The investigator must agree to make any required progress reports to the IRB, as well as reports of SAEs, life-threatening conditions, or death.

9.2 ETHICAL CONDUCT OF THE STUDY

All clinical work conducted under this protocol is subject to GCP guidelines. This includes an inspection by Sponsor or its designee, health authority or IRB/IEC representatives at any time. The investigator must agree to the inspection of study-related records by health authority representatives and/or Sponsor or its designee.

The study will be conducted in accordance with the following guidelines:

- GCP: Consolidated Guideline (International Conference on Harmonization of Technical Requirements for the Registration of Pharmaceuticals for Human Use, May 1996)
- Declaration of Helsinki: Brazil, 2013
- Israeli MOH guidelines (February 2016)
- Guidelines from the country-specific National Competent Authority as appropriate

9.3 PROTOCOL REVISIONS AND/OR DEVIATIONS

Changes to the protocol may be made only by the Sponsor. All protocol modifications must be submitted to the IRB/IEC in accordance with local requirements and, if required, to Regulatory Agencies, either as an amendment or a notification. Approval for amendments must be granted before any changes can be implemented, except for changes necessary to eliminate an immediate hazard to trial study patients, or when the changes involve only logistical or administrative aspects of the trial. No approval will be required for notifications.

9.4 STUDY PATIENT INFORMATION AND CONSENT

Prior to study screening, each study patient will be informed in detail about the study drug to be administered and the nature of the clinical investigation with its expected risks and discomforts. The basic elements of informed consent as specified by the FDA (21 CFR 50.25) and ICH-GCP will be followed. Written consent will be obtained from each study patient or their legally authorized representative to be involved in the clinical trial by using the IRB/IEC-approved ICF prior to the conduct of any study-related activity. Each study patient will be given a copy of the

written ICF. The study patients will also be instructed that they are free to withdraw their consent and discontinue their participation in the study at any time without prejudice. Each study patient's chart will include the signed ICF for study participation. When the study treatment is completed and the CRF has been monitored, the ICF will be kept in the investigator's central study file for the required period. Regulatory authorities may check the existence of the signed ICF in this central study folder if not confirmed during the study.

9.5 STUDY PATIENT INSURANCE

The Sponsor has an insurance policy for the total duration of the study covering the patients and investigators in respect of the risks involved in conducting this study according to this protocol. The certificate of insurance will be filed in the investigator's file or can be made available to the investigator and to the IRB/IEC upon request.

9.6 PERSONAL DATA PROTECTION

The Sponsor complies with the principle of study patient's right to protection against invasion of privacy. Throughout this trial, all data will be identified only by a subject number and study patient initials. The identifying patient data will be blinded in all data analyses. However, the patient must be informed and consent is required that authorized personnel of the Sponsor and/or designee (Study Monitor, Auditor, etc.) and relevant health regulatory agency will have direct access to personal medical data to assure a high quality standard of the study.

10.0 DATA COLLECTION, MANAGEMENT AND QUALITY ASSURANCE

10.1 AUDITS AND INSPECTIONS

The investigator should understand that source documents for this trial should be made available to appropriately qualified personnel from the Sponsor or its designees or to regulatory authority inspectors after appropriate notification. The verification of the CRF data must be by direct inspection of source documents. These audits or inspections may take place at any time, during or after the study, and are based on the national regulations, as well as ICH guidelines.

10.2 STUDY MONITORING

Monitoring of the study is the responsibility of the Sponsor and may be delegated to a CRO or a contract monitor. The study monitor will advise the investigator regarding the practical conduct of the study and maintaining compliance with the protocol, GCP and all applicable regulatory requirements. Throughout the course of the study, the study monitor will oversee the conduct and the progress of the study by frequent contacts with the investigator. This will include telephone calls and on-site visits. During the on-site visits, the CRF will be reviewed for completeness with corresponding source documents. As part of the data audit, source documents will be made available for review by the study monitor. The study monitor will also perform drug accountability checks and may periodically request review of the investigator's study file to ensure completeness of documentation in all respects of clinical study conduct.

Upon completion of the study, the study monitor will arrange for a final review of the study files after which the files should be secured for the appropriate period. The investigator or appointed delegate will receive the study monitor during these on-site visits, cooperate in providing the documents for inspection and respond to inquiries.

10.2.1 Source Data and Records

Source data/records contain all the information which is necessary for the reconstruction and evaluation of the study. Source data/records are 1) original records, 2) certified copies of original records, 3) observations, 4) laboratory reports, 5) paper Case Report Forms (CRFs) and/or data sheets. Source data/records are to be kept within the control of the investigator until the end of the contractual retention period. The investigator will permit study-related monitoring, audit(s), IRB review(s) and regulatory inspection(s), with direct access to all the required source records.

10.3 QUALITY LABORATORY STANDARDS

Laboratory tests or evaluations described in this protocol will be conducted in accordance with quality laboratory standards as described in the SOPs of the local institution laboratory and central laboratories.

10.4 DATA COLLECTION AND MANAGEMENT

All aspects of the study will be monitored by Immune Pharmaceuticals and their designees according to Good Clinical Practices (GCP) and Standard Operating Procedures (SOPs) for compliance with applicable government regulation (i.e., Informed Consent Regulations [US 21CFR, Part 50] and Institutional Review Board regulations [US 21CFR, Part 45.103]). Access to all records, both during the trial and after trial completion, should be made available to Immune Pharmaceuticals at any time for review and audit to ensure the integrity of the data.

The investigator must conduct the protocol in accordance with applicable GCP regulations and guidelines. Every attempt must be made to follow the protocol and to obtain and record all data requested for each subject at the specified times. If data is not recorded per protocol, the reasons must be clearly documented in the CRF and site records.

Prior to the study, an Immune Pharmaceuticals representative will review the protocol and study procedures and processes to include IP receipt, storage, and accountability; investigator responsibilities and staff adequacy; event reporting timelines; monitoring and audit requirements; study documentation responsibilities; subject enrollment procedures; and CRF requirements to include system training with the investigator and site staff. Additional tasks and activities may be completed as needed for the study.

During the study, all protocol-specified data will be recorded in the source documents and data will be entered on the CRF from the source documents. Checks will be performed by the study monitor and data management to ensure the quality, consistency, and completeness of the data. Instances of missing or un-interpretable data will be resolved with the site staff. Site personnel will be responsible for providing resolutions to the data queries and to correct the CRFs, as appropriate.

